#### **5.4.6. Pharmacokinetic Period**

There is no defined PK period in this study.

#### **5.4.7. Follow-up Period**

The follow-up period is defined as the period 14 (+7) days after the last dose of rFIXFc.

### **5.5. Handling of Missing Data**

Aside from the following, no imputation of study data will be performed.

The occurrence of a new bleeding episode will be imputed if >72 hours lapse between 2 consecutive injections administered to treat bleeding. Details are provided in Section 7.4.1.

For the analysis of AEs and concomitant medications/procedures, if the stop/start date of an AE/concomitant medication is missing or partial, the corresponding study day will be left blank. However, inferences will be made from the partial and missing dates to classify medications as prior and/or concomitant and AEs as treatment emergent (or not). These inferences are described in Sections 6.4.1 and 9.3.1, respectively.

For patients in the ITI Subgroup, determination of response requires baseline IR. If this is missing, an absolute value is employed. Further details can be found in Section 7.4.9.

	Statistical Analysis Plan	Final v1.0
---	----------------------------------	-------------------

## 5.6. Electronic Patient Diary (EPD) Data

Patient recorded diary data was within this project, previously queried via a defined process which required confirmation with the patient of all changes. Taking into consideration audit findings and industry standards to control changes to patient reported data, the query process was updated to allow only changes defined as not requiring patient confirmation. No changes which were not allowable under this new process were made to the EPD data. Although consolidation of records of single vials recorded within 60 minutes of each other (SVC/L60) was classified as a change not requiring patient confirmation (as agreed with MHRA in 2014), these changes are no longer being made directly into the data, but will be applied via a programmatic data convention. In addition, true duplicate records resulting from administrative issues and hence not requiring patient confirmation of the change will be deleted. The exception to this is where both injections are in the eCRF, which do not require patient confirmation, as site notes provide an alternative source and so these can be queried and processed as per the previous process.

These programming algorithms to address these two scenarios are described as follows:

### 1) Record consolidation:

When a dose requires more than one vial and these vials are erroneously recorded in the EPD/eCRF as separate injections, albeit within a short time window, the change to consolidate these multiple records into one record is called Single Vial Consolidation (SVC). Based on the EPD set up, the programming algorithm to identify and consolidate the records is as follows:

- Identify all injection records within 60 minutes of one another where the variables (injection date/times, lot numbers, number of vials, and vials strength in nominal IU) are not exactly the same on each record. There are four scenarios:
  - Date and time of injections are not exactly same, and lot numbers, number of vials, and vials strength in nominal IU are not the same.
  - Date and time of injections are not exactly same, but lot numbers, number of vials, and vials strength in nominal IU are the same.
  - Date and time of injections are exactly same, but lot numbers, number of vials, and vials strength in nominal IU are not the same.
  - Date and time of injections are exactly same, and lot numbers, number of vials, and vials strength in nominal IU are the same, and these duplicates occurred for reasons which cannot be attributed to administrative issues as specified below.
- Consolidate injections as follows:
  - Record with earliest injection date/time retained with corresponding contextual information.
  - Combine/sum values related to the dose (e.g. lot numbers, number of vials, volume injected, nominal and actual dose) into the single retained record.

	Statistical Analysis Plan	Final v1.0
---	----------------------------------	-------------------

If injections identified with the above algorithm have distinctly different reasons (e.g., one injection is recorded as bleeding or surgery and another is recorded as prophylaxis, additional, or OTHER), then the records should NOT be consolidated. However if one reason is missing, then consolidation can be performed.

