10.2.3.2. Information to be Recorded for Bleeding Episodes

Subjects or their parent/caregiver must be issued with an EPD once eligibility has been confirmed and they have been enrolled; from that point forward, all data regarding bleeding episodes and injections administered for a bleeding episode for doses administered at the subject's home or at locations other than the study site must be entered into the EPD. The incidence of bleeding in this study will be obtained from EPDs, eCRFs, and medical records. If a subject has enrolled in the study, information from medical records on dosing and bleeding episodes treated with commercially available rFIXFc prior to the subject being issued with an EPD should be recorded in the eCRF, according to the eCRF Completion Guidelines.

It is recommended that subjects or parents/caregivers enter bleeding episode information into the EPD immediately after an injection.

The Investigators and Clinical Monitors will ensure that there is consistency in bleeding episode data between the subject's medical record, IXRS, source documents, EPD, and eCRFs. During the clinic visits and monthly telephone calls with the subject's parents/caregivers, the subject/parent/caregiver will be reminded about timely EPD completion and the Investigator will verify whether or not a bleeding episode has occurred, and was "spontaneous" or "traumatic" (Section 10.2.3.1).

If, following this discussion, the Investigator judges that the classification by the subject's parents/caregivers was incorrect, the Investigator will document it in the subject's medical records with the rationale for the new classification, and the eCRF, documenting the new classification of the bleeding episode according to the Investigator and whether or not the subject's parents/caregivers agreed with this new classification. With regard to dose changes, the Investigator's classification of spontaneous or traumatic will be used (if different from the classification recorded in the EPD by the parent/caregiver). Both spontaneous and traumatic bleeding episodes will be collected.

Information collected in the EPD will include, but not be limited to, the following:

- the type of bleeding episode (e.g., spontaneous, traumatic) and if related to sports activity or physical activity
- the date the bleeding event occurred
- the dose administered to treat the bleeding episode including any repeat doses
- the location of the bleed

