#### Bleeding Episode

A bleeding episode is defined as follows: A bleeding episode starts from the first sign of a bleed, and ends no more than 72 hours after the last injection to treat the bleed, within which any symptoms of bleeding at the same location, injections  $\leq 72$  hours apart, are considered the same

	Statistical Analysis Plan	Final v1.0
---	----------------------------------	-------------------

bleeding episode. Any injection to treat the bleeding episode, taken >72 hours after the preceding one, will be considered the first injection to treat a new bleeding episode in the same location. Any bleeding at a different location is considered a separate bleeding episode, regardless of the time from the last injection.

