## 2) True duplicates removal:

When injections are identified in the EPD with exactly the same date/times, lot numbers, number of vials, and vials strength in nominal IU, these may have resulted due to administrative issues and are therefore true duplicates. There are three types of administrative issues as follows:

- Technical transmission issue
- Entry of same record into 2 different devices
- Records duplicated in EPD and eCRF which remain despite attempts to correct the data via the query process

The programming algorithm to identify and delete the duplicates is as follows:

- Identify all injections that have exactly the same date/times, reasons for injection, lot numbers, number of vials, and vials strength in nominal IU
- Remove the duplicates and keep a single record

As with SVC, if injections identified as duplicates have distinctly different reasons (e.g., one injection is recorded as bleeding or surgery and another is recorded as prophylaxis, additional, or OTHER), then these cannot be considered duplicates and removed. However if one reason is missing, then they can be considered duplicates and removed.

	Statistical Analysis Plan	Final v1.0
---	----------------------------------	-------------------

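### SAP 5.6 can merge bleed-treatment records that name different locations, and so can drop an episode that SAP 5.2.4 and Protocol 10.2.3.1 count separately

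*SAP*

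**What the plan says.** SAP 5.6 replaces manual diary corrections with two programmed rules.

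- **Consolidation.** The stated purpose is narrow: "When a dose requires more than one vial and these vials are erroneously recorded in the EPD/eCRF as separate injections". The instruction is broader: "Identify all injection records within 60 minutes of one another". Records qualify when time, lot, vial count or vial strength differ. They also qualify when all four agree but the repetition cannot be put down to an administrative cause. Dose quantities are added up, and for everything else the rule is "Record with earliest injection date/time retained with corresponding contextual information".
- **Duplicate removal.** The instruction is "Identify all injections that have exactly the same date/times, reasons for injection, lot numbers, number of vials, and vials strength in nominal IU"; one record is then kept.
- **The bar to merging.** Both rules stand down when the injections "have distinctly different reasons (e.g., one injection is recorded as bleeding or surgery and another is recorded as prophylaxis, additional, or OTHER". If one of the two reasons is missing, the merge goes ahead.

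Bleed location appears in neither rule. It is available, because Protocol 10.2.3.2 lists "the location of the bleed" among the diary items. The episode definition in SAP 5.2.4, repeated in Protocol 10.2.3.1, depends on it: "Any bleeding at a different location is considered a separate bleeding episode, regardless of the time from the last injection".

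**The concern.** The variable that separates one episode from another is not consulted when records are merged. Suppose a caregiver logs a knee bleed and an elbow bleed as two records 20 minutes apart, both with the same bleeding reason. Under the algorithm they become one record carrying the knee's details. The elbow's location, type and response rating have no stated place to go.

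The SAP ties bleeds closely to injections, so losing a record could mean losing a bleed:

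- SAP 6.6.1.1 carries spontaneous and traumatic bleed as reasons for injection.
- SAP 7.4.8 builds each episode from an initial injection plus its follow-ups.
- SAP 5.5 imputes a new episode from the gap between bleed-treatment injections.
- SAP 7.4.5 tabulates response by injection.

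At stake are overall ABR, ABR by location, spontaneous joint ABR (a secondary endpoint, exposed when the joint record is the later of the pair) and the response summaries. There is a related dose problem. If one physical dose is entered twice to log two sites, and this is not classed as administrative, consolidation adds the dose to itself. That would inflate consumption (SAP 6.6.1.4) and dose per injection (SAP 7.4.8).

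**Working it through.** The plan gives no figure on this point, so there is none to reproduce. The check has three parts.

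**1. Both texts applied to mock records.** The merge rule was coded as written: within 60 minutes, same or missing reason, earliest details kept. The episode definition was also coded: a new episode at a different location, or more than 72 hours after the last injection at the same location. All mock records have bleeding as the reason.

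| Mock records | Episodes, unmerged | After SAP 5.6 | After SAP 5.6 with a location bar |
|---|---|---|---|
| A. Two vials, same site, 20 min apart | 1 | 1 | 1 |
| B. Two sites, 20 min apart | 2 | 1 | 2 |
| C. Two sites, identical time, lot, vials, strength | 2 | 1 | 2 |
| D. Two sites, 90 min apart | 2 | 2 | 2 |
| E. As B, plus an injection at the second site at 48 h | 2 | 2 | 2 |

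An episode is lost in B and C only. Four conditions must therefore hold together:

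- The two sites are entered as separate records within 60 minutes, or as identical records.
- The reasons do not block the merge.
- Episodes are counted from the merged record.
- No later injection is recorded separately for the second site.

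The location bar restores the episode in B and C and still consolidates genuine vial-splitting in A.

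**2. Effect of one lost episode.** SAP 7.4.3 defines ABR as episodes ÷ efficacy-period days × 365.25, so the loss per episode is 365.25 ÷ days:

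- six months: 365.25 ÷ 182.625 = 2.00
- 50 weekly doses, i.e. 49 intervals × 7 = 343 days: 365.25 ÷ 343 = 1.07
- one year: 365.25 ÷ 365.25 = 1.00
- two years: 365.25 ÷ 730.5 = 0.50

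For scale only, Protocol 5.1.1 cites background rates of 3 to 4 spontaneous bleeds a year on prophylaxis and about 20 bleeds a year on episodic treatment. Over one year, one lost episode is 1/3 = 33%, 1/4 = 25% or 1/20 = 5% of those rates.

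**3. Effect on a mean ABR.** Let f be the share of episodes that are second-site records lost in this way. The reported ABR is then true ABR × (1 − f). The documents do not give f, so these values are assumptions:

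| f (assumed) | True ABR 4 | True ABR 20 |
|---|---|---|
| 0% | 4.00 | 20.0 |
| 1% | 3.96 | 19.8 |
| 5% | 3.80 | 19.0 |
| 10% | 3.60 | 18.0 |

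**The case against.** The strongest reply is that SAP 5.6 concerns injection records and nowhere says that a bleeding episode is deleted. Bleeds are derived under SAP 7.4.1, which points back to the definition with its location rule, and the SAP's output list keeps bleed-level listings apart from injection-level ones. The diary set-up is not described: one record may hold several sites, or bleeds may sit in their own table. This stands as a limit on the claim. A reader might infer that multi-site bleeds generally lose an episode and that the reported ABR is understated by some percentage. The documents do not support that, because they establish neither the record structure nor any multi-site frequency.

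Other replies stand in part:

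- **True duplicates are confined to administrative causes.** The introduction to that rule says so, and a deliberate entry per site is not such a cause. But the operational step does not repeat the limit, and an identical pair not removed there passes to consolidation, which also ignores location.
- **Spontaneous and traumatic bleeds may already count as distinctly different reasons.** They may; the SAP does not say. Two sites with the same type are not protected either way.
- **The 60-minute consolidation was agreed with a regulator, and investigators verify bleeds at visits and monthly calls.** The agreement as described covers records of single vials. The merge is applied afterwards by program, without patient confirmation.
- **ABR is secondary and descriptive.** True. The primary endpoint, inhibitor development, is untouched, which limits the weight of the point.

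**Conclusion.** The conflict between the rules is real, but its effect is conditional. As written, SAP 5.6 can reduce two bleed-treatment records at different locations to one, while the plan's own definition counts two episodes. No passage says how the second location is kept.

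Where all four conditions hold, the loss is one episode: 1.0 on a child's ABR over one year, 2.0 over six months. A dropped episode can only lower overall ABR, which flatters the product. With about 30 children planned and possibly low bleed rates, a few such events could show in the summaries.

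The total effect cannot be computed from the documents and may be zero. The percentages in the last table above are illustrations, not estimates. The point is worth correcting because a stated rule can contradict a stated definition, not because a bias has been shown.

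**What to change.** Make the change in the paragraph of each algorithm that bars merging for different reasons. Adding location to the consolidation rule's list of selection variables would not help, because those variables pick out records that differ and do not stop a merge. Add that:

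- Bleed-treatment records with different recorded locations are not reduced to one episode.
- The dose is combined if the records are vials of one injection, and counted once if the same dose was logged twice.
- Each location, with its type and response, is kept as an episode linked to that injection.

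Also state whether spontaneous versus traumatic is a distinctly different reason. Report the number of merges across locations, with a sensitivity ABR on the unmerged episodes. If the diary already holds several sites per record, or stores bleeds separately, a sentence saying so closes the point.

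The cost is a sentence or two in each algorithm and a small programming change before database lock, with no new data. There is one small downside: vials of a single dose entered with inconsistent locations could add an episode. The reported count of cross-location records would show this.

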## 2) True duplicates removal:

When injections are identified in the EPD with exactly the same date/times, lot numbers, number of vials, and vials strength in nominal IU, these may have resulted due to administrative issues and are therefore true duplicates. There are three types of administrative issues as follows:

- Technical transmission issue
- Entry of same record into 2 different devices
- Records duplicated in EPD and eCRF which remain despite attempts to correct the data via the query process

The programming algorithm to identify and delete the duplicates is as follows:

- Identify all injections that have exactly the same date/times, reasons for injection, lot numbers, number of vials, and vials strength in nominal IU
- Remove the duplicates and keep a single record

As with SVC, if injections identified as duplicates have distinctly different reasons (e.g., one injection is recorded as bleeding or surgery and another is recorded as prophylaxis, additional, or OTHER), then these cannot be considered duplicates and removed. However if one reason is missing, then they can be considered duplicates and removed.

	Statistical Analysis Plan	Final v1.0
---	----------------------------------	-------------------

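### The programmed duplicate-deletion step in SAP 5.6 has no cause condition, so it also deletes identical injection records that the consolidation rule says to sum, and a real two-vial dose can be halved

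*SAP*

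**What the plan says.** SAP 5.6 replaces manual diary corrections with two programmed conventions.

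**Rule 1, record consolidation (Single Vial Consolidation).** It repairs doses of more than one vial that were entered as separate injections. Its lead-in takes records within 60 minutes of one another whose listed variables "are not exactly the same on each record". Four scenarios follow. The fourth covers records that agree on date/time, lot, number of vials and strength, provided that "these duplicates occurred for reasons which cannot be attributed to administrative issues as specified below". The action is to "Combine/sum values related to the dose (e.g. lot numbers, number of vials, volume injected, nominal and actual dose) into the single retained record".

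**Rule 2, true duplicates removal.** The opening of 5.6 gives its scope: "true duplicate records resulting from administrative issues and hence not requiring patient confirmation of the change will be deleted". The rule names three administrative causes: a transmission problem, "Entry of same record into 2 different devices", and a record left in both the EPD and the eCRF after querying. Of identical records it says that "these may have resulted due to administrative issues and are therefore true duplicates". Its algorithm has two steps: "Identify all injections that have exactly the same date/times, reasons for injection, lot numbers, number of vials, and vials strength in nominal IU", then "Remove the duplicates and keep a single record".

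Under both rules, records with clearly different reasons are left alone, and a pair with one missing reason may still be processed.

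**The concern.** The SAP separates the two rules by the cause of the duplication. The consolidation rule states that condition in its fourth scenario. The deletion rule states it in its introduction but not in the steps to be programmed. The text moves from a possible administrative cause to a conclusion that the records are true duplicates, with no test in between. No variable, flag, adjudication step or rule order is given to establish cause.

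A programmer who follows the deletion steps literally removes every identical same-reason set, and the fourth consolidation scenario is left with no same-reason records to act on. The consolidation rule does not prevent this, because its lead-in excludes identical records while its fourth scenario requires them.

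The records at risk are of the kind consolidation exists to repair: one dose, two equal vials, two entries. Consumption is a secondary objective, and annualized consumption and dose per injection to resolve a bleed are secondary endpoints (SAP 2.1.2 and 2.2.2). Deletion also goes beyond its own justification, since 5.6 permits it without patient confirmation on the ground that the cause is administrative.

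**Working it through.** The plan states no figure for this step, so the check is a comparison of the rules followed by dose arithmetic.

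**Inputs**
- Rule wording: SAP 5.6.
- Vial strengths 250, 500, 1000 and 2000 IU, with whole vials for prophylaxis and bleeds: Protocol 10.1.1.
- Recommended initial prophylaxis 50 IU/kg weekly: SAP 3.1.2.2.
- Annualized consumption = total nominal IU/kg / days in the efficacy period × 365.25: SAP 6.6.1.4.
- A dose is compliant within 80%-125% of the prescribed dose; a patient is compliant with a rate of at least 80%: SAP 6.6.2.2.
- Assumed, not in the documents: a body weight of 10 kg (illustration only) and the share *f* of doses affected.

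**Step 1: which rule takes which records.** Cross same or different date/time, same or different lot/vials/strength, and administrative or other cause, for records within 60 minutes with the same reason. This gives 2 × 2 × 2 = 8 cells.

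| Records | Cause | Consolidation scenarios | Deletion steps |
|---|---|---|---|
| Not identical (6 cells) | either | sum | not selected |
| Identical (1 cell) | administrative | excluded by scenario 4 | keep one |
| Identical (1 cell) | not administrative | sum (scenario 4) | keep one |

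Only the last row is claimed twice, with opposite results. If the consolidation lead-in is taken as governing, that row is not consolidated at all and only deletion applies.

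**Step 2: effect on one dose.** A true dose of 2 × 250 IU at 10 kg is 500/10 = 50 IU/kg. With one record deleted it is 250/10 = 25 IU/kg, and 25/50 = 50% of the true dose. The ratio does not depend on weight. If the dose was taken as prescribed, 50% is below the 80% lower limit.

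**Step 3: effect on consumption.** At 50 IU/kg weekly, annualized consumption is 50 × 365.25/7 = 2609 IU/kg. With a share *f* halved it is 2609 × (1 − 0.5*f*):
- *f* = 2%: 2583 (−1.0%)
- *f* = 5%: 2544 (−2.5%)
- *f* = 20%: 2348 (−10%)
- *f* = 100%, the limit for a family that always logs this way: 1304 (−50%)

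**Step 4: effect on dose compliance.** Take an otherwise fully compliant patient with 50 weekly doses. With 10 doses affected the rate is 40/50 = 80%, still compliant. With 11 it is 39/50 = 78%, not compliant.

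**Step 5: what does not move.** Either rule leaves one record at the same time. Injection counts, exposure days, ABR and the inhibitor endpoint are therefore the same under both.

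**The case against.** The strongest reply is that the SAP does name the separator. The opening of 5.6 limits deletion to administrative duplicates, the deletion rule lists three causes, and scenario 4 states the condition within the consolidation rule. On this reading only a repetition in the two programming steps is missing. That describes the defect correctly, but it does not remove it: those steps are what gets programmed, and no source for cause is named.

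The conflict is also narrow, and this stands. It needs equal vials from one lot, logged separately at the same minute, with the same reason or one reason missing. The strengths form a doubling series, so any dose in 250 IU steps up to 250 + 500 + 1000 + 2000 = 3750 IU can be made without repeating a strength. At 50 IU/kg that is 3750/50 = 75 kg, in a trial of mostly very young children (SAP 3.3). Unequal vials differ in strength and go to consolidation only. Equal-vial doses remain possible, because nothing in the protocol or SAP requires the fewest vials, but they need not be common.

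Other safeguards exist. Pairs wholly within the eCRF are queried against site notes (SAP 5.6), sites and monitors reconcile dosing across sources (Protocol 10.1.2), and vials are returned for accountability (Protocol 12.1.4). They may reduce the number of such records, but they do not say how the program should treat those that remain.

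A reader might infer that the rules conflict in both directions, so that a true duplicate could equally be summed and a dose doubled. The text does not support this for identical records. Scenario 4 expressly excludes administrative duplicates, and summing one would require the further assumption that its cause went unrecognised.

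**Conclusion.** The point holds as a one-directional conflict. Followed literally, the deletion steps capture the identical, non-administrative records that scenario 4 says to sum, and a real two-vial dose is recorded at 50% of its IU. Dose per injection, total dose per bleed, average weekly dose and annualized consumption are understated, and dose compliance is affected.

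The 50% per two-vial dose follows from the rules. The effect on totals rests on an assumed share of affected doses: −1% at 2%, −2.5% at 5%, more for a single patient whose family habitually logs this way. All affected outputs are descriptive, and the primary endpoint is untouched. The change is still worth making, because a stated rule gives a wrong dose in secondary endpoints and correcting it is cheap. The list of listings in SAP 12 names none for deleted or consolidated records, so a reader of the report could not see what had been done.

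**What to change.** 1. Add to the deletion rule's selection step the condition that one of the three listed administrative causes is established, and name the data source for each: for example, one EPD plus one eCRF record, or a documented transmission fault or two-device entry.
2. Reword the consolidation lead-in so that it admits scenario 4, and apply deletion before consolidation. Each identical set then falls under exactly one rule, and a real two-vial dose keeps 100% of its IU.
3. Set one fixed default for identical sets of undetermined cause. Under scenario 4 as written, that is to consolidate and sum. The default should not be the version closer to the prescribed dose, because dose compliance is measured against that dose and would rise by construction. Check these sets against vial accountability where available, list them, and repeat consumption and dose compliance under the alternative handling. The repeat matters because summing would overstate the dose if such a set were in fact a duplicate.

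The cost is SAP wording, programming, one listing and one sensitivity analysis, best settled before database lock. The documents do not say that device or transmission identifiers are in the analysis data. Where they are not, the default in item 3 applies.
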